2.3 Change in planned analyses from the protocol

Cardiac imaging is only collected post baseline where clinically indicated and the value and potential abnormality will only be listed, and not summarized.

Summaries will be conducted for all patients combined with the following exceptions –

- Primary efficacy analysis on the clinical benefit via Bayesian hierarchical model
- Other clinical benefit and tumor response summaries for tumor types that have 10 or more patients enrolled.

In the event of a low response rate, DOR will be listed only.

2.5 Definitions

2.5.1 Study drug

Study drug = ribociclib 600 mg once daily, 3 weeks on and 1 week off in a cycle of 28 days.

2.5.2 Date of first administration of study drug

The date of first administration of study drug is defined as the first date when a nonzero dose of study drug is administered and recorded on the dose administration electronic case report form (eCRF). The date of first administration of study drug will also be referred as start of study drug.

2.5.3 Date of last administration of study drug

The date of last administration of study drug is defined as the last date when a nonzero dose of study drug is administered. Last date of study drug will also be referred as end of study drug.

2.5.4 Study day

The study day, describes the day of the event or assessment date, relative to the reference start date (date of first administration of study drug).

The study day will be calculated as the difference between the date of the assessment and the start of study treatment plus 1. If the date of the assessment is before the start of study treatment the study day will be negative and will be calculated as the difference between the date of the assessment and the start of study treatment.

2.5.5 Baseline

In general, the last available assessment before or at date of start of study treatment will be used as the 'baseline' assessment. For electrocardiogram (ECG), the average of the triplicate assessments prior to the first administration of study drug will be used as the 'baseline' assessment. In the event of missing pre-dose ECG time-point on the day of study treatment start, the screening ECG assessment will be used as the baseline.

2.5.6 On treatment assessment

On-treatment assessment is defined as any assessment obtained in the time interval: Date of first administration of study treatment through the date of last administration of study treatment + 30 days. If the patient is still on treatment at the time of the cut-off, on-treatment assessments include any assessment recorded in the database up to the cut-off and which occur after the start date of study treatment.

Data listings will include all assessments, flagging those which are not on-treatment assessments.

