Physical examination for assessment of Extramedullary disease or Organomegaly (if present)	D	7.2.1.4.3	X	X	X	X	X	X		X			
Bone Marrow Biopsy or aspirate	D	7.2.1.4.2	X	To confirm response of CR or if clinically indicated									
History/assessment of chromosomal abnormalities/Karyotype	S	7.2.1.4.4	X 										
Evaluation of transfusion dependency	D	7.2.1.4.5	X	X	X	X	X	X		X			
Myeloproliferative Neoplasm (MPN) Symptom Assessment	D	Appendix Q	X	X	X	X	X	X		X			

	Category	Reference to assessment	Screening phase	Treatment Phase						Post treatment follow-up phase	Survival phase
				C1		C2		Subsequent cycles			
Visit Number			1	2	3	4	5	6	777	501	701
Cycle days 			-28 to -1	1	15	1	15	1		EOT + 30 ( $\pm 4$ ) days	EOT + every 3 months 

. A complete cycle is defined as 28 days.  
. Additional survival assessments may be performed outside the 3 months follow-up schedules if a survival update is required for an interim assessment to meet safety or regulatory needs.  
3. Tumor assessments at EOT are required for patients who discontinue study treatment before the first scheduled post-screening tumor assessment and for patients whose previous tumor assessment did not demonstrate PD and was done at least 8 weeks ( $\pm 4$  days) prior to end of treatment visit.  
4. These assessments should be performed only if the screening assessment occurred > 4 days from Cycle 1 Day 1. The patient must continue to meet all eligibility criteria on C1D1, as they did during the screening period.  
5. Tumor assessments include CT/MRI of the chest abdomen and pelvis at all timepoints. Tumor assessments are described in [Section 7.2.1](#).  
6. Women of childbearing potential must undergo a serum pregnancy test at screening and EOT. Women of child-bearing potential will undergo a monthly urine pregnancy tests during the study.  
7. For patients who have a response of PR or greater, a confirmation assessment must be performed at least 4 weeks after the initial observation.  
8. The frequency of disease assessment will be reduced to every 16 weeks after patient have completed 16 weeks on treatment.  
9. Skin lesions should be documented using a digital camera (color photography) in clear focus showing the ruler or calipers and the corresponding measurement in such a way that the size of the lesion(s) can be determined from the photograph  

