4.6 Clinical Benefit Rate by Gene Mutations

The concordance between gene mutations detected by local and central labs will be summarized on protocol pre-defined mutations. A frequency summary will be provided for summarizing clinical benefit rate per gene mutation using mutation data provided by the central lab (on protocol pre-defined mutations only) as well as local lab. The data will also be presented in a listing.

5 Safety evaluation

The assessment of safety will be based mainly on the frequency of adverse events and on the number of laboratory/ECG values that fall outside of pre-determined ranges. Other safety data (e.g. vital signs) will be considered as appropriate.

All safety outputs will use the safety set. The safety summary tables will only include “on-treatment” assessments (see the definition of “on-treatment” in Section [2.5.6](#)), i.e. those collected on or after the first date of study treatment and collected no later than 30 days after the date of last study treatment administration. The AEs started before the first dose but worsened during the treatment are also considered as ‘on-treatment’ events. All safety assessments will be listed and those collected later than 30 days after the last treatment/exposure date will be flagged.

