5.3 Laboratory evaluations

Laboratory assessment will be collected at screening and post baseline (at scheduled visits outlined in the protocol or as clinically indicated). The collected laboratory values will be converted into standard units and the severity grade will be calculated using CTCAE v4.03. A severity grade of 0 will be assigned when the value is within normal limits. For laboratory parameters where severity grades are determined both through normal limits and absolute cut-offs, in the unlikely case that a local laboratory normal range overlaps into the higher (i.e., non-zero) CTCAE grade, the laboratory value will still be taken as within normal limits and assigned a CTCAE grade of zero.

Abnormal on-treatment laboratory values will be summarized using shift tables (from baseline to any abnormal laboratory value post baseline) by each laboratory parameter at its worst severity grade. The number and percentage of patients with abnormal laboratory values will be presented by CTCAE grade for each laboratory parameter that is CTCAE gradable. For laboratory parameters where CTCAE grades are not defined, shift tables using the low/normal/high/(low and high) classification to compare baseline to the worst on-treatment value will be provided. Listings of all laboratory values (blood chemistry, hematology/coagulation parameters separately) in chronologic order will be provided for each laboratory parameter. Laboratory values collected more than 30 days after study treatment discontinuation will be flagged in the listing. Separate listings will also be provided for notable laboratory abnormalities (i.e., grade 3 or 4 laboratory toxicities post start of study treatment for CTC gradable parameters, or abnormal laboratory values for non-CTC gradable parameters). In addition, other lab tests such as those for urinalysis and pregnancy will be listed separately.

Patients' hepatic toxicity will be evaluated for on-treatment liver parameter values. The worst case assessments are used for the analyses. The number and percentage of patients who met the following categories of the criteria will be presented.

- ALT > 3xULN, ALT>5xULN, ALT>8xULN, ALT>10xULN, ALT>20xULN, separately
- AST >3xULN, AST>5xULN, AST>8xULN, AST>10xULN, AST>20xULN, separately
- ALT>3xULN or AST>3xULN, ALT>5xULN or AST>5xULN, ALT>8xULN or AST>8xULN, ALT>10xULN or AST>10xULN, ALT>20xULN or AST>20xULN, separately
- TBILI>ULN, TBILI>2xULN, separately

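### The first-dose date lies in both the baseline and the on-treatment window, so a pre-dose Day 1 laboratory value can count as on-treatment in the hepatic threshold table and the non-CTCAE shift tables

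*SAP*

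**What the plan says.** SAP 2.5.4 numbers the date of first dose as Day 1. Four statements in the SAP then decide where a Day 1 record goes.

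- Baseline (2.5.5) is "the last available assessment before or at date of start of study treatment". A pre-dose condition is added for ECG only.
- The general on-treatment window (2.5.6) is "Date of first administration of study treatment through the date of last administration of study treatment + 30 days".
- For patients still on treatment at cut-off, 2.5.6 says that on-treatment assessments "include any assessment recorded in the database up to the cut-off and which occur after the start date of study treatment".
- The opening of Section 5 describes the contents of the safety summary tables as "those collected on or after the first date of study treatment", up to 30 days after the last dose. It makes no exception for ongoing patients.

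SAP 5.3 uses this window for the liver tables: "hepatic toxicity will be evaluated for on-treatment liver parameter values. The worst case assessments are used for the analyses". It also compares baseline with the worst on-treatment value in the shift tables for parameters that have no CTCAE grade.

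The protocol determines when a Day 1 laboratory value exists. Table 7-1, footnote 4: "These assessments should be performed only if the screening assessment occurred > 4 days from Cycle 1 Day 1". Section 7.1.2 likewise requires older screening laboratory tests to be repeated on the first dosing day. The protocol glossary places baseline before the first dose on that day.

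**The concern.** A worst-case table is meant to describe what happened under the drug. If the window over which the worst value is taken also contains the pre-treatment value, each count can only stay the same or rise, and any rise is not treatment-related. Whether a patient is exposed to this depends on how old the screening tests were: a patient screened 3 days before dosing has no Day 1 draw, while one screened 10 days before does.

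The plan also gives two answers for patients still on drug at cut-off. A programmer following 2.5.6 and one following Section 5 would build different tables from the same data.

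The ongoing-patient sentence also errs in the other direction. Read literally, it removes the genuine post-dose Day 1 ECGs at 2, 4 and 6 h (protocol Table 7-2) from on-treatment for those patients. Protocol 1.2.1.1.3 names hepatic toxicity and QT prolongation among the major potential toxicities, so these are outputs that readers will consult.

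**Working it through.** The plan states no figure on this point, so there is none to reproduce. The check applies the windows literally and then compares the eligibility limits with the table cut-points.

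**Step 1. Windows by study day** (Day 1 = date of first dose; last dose assumed on Day 84, so the window closes on Day 84 + 30 = 114).

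| Study day | Baseline (2.5.5) | On-treatment, off drug at cut-off (2.5.6) | On-treatment, still on drug (2.5.6) | On-treatment (Section 5) |
|---|---|---|---|---|
| -5, -1 | yes | no | no | no |
| 1 | yes | yes | no | yes |
| 2, 15 | no | yes | yes | yes |

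The overlap is exactly Day 1, and Day 1 is also the only day on which 2.5.6 and Section 5 disagree.

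**Step 2. Which hepatic rows an eligible pre-dose value can reach.** Limits are from protocol 5.2, criterion 13. Protocol 6.1.1 requires eligibility still to hold on Cycle 1 Day 1. Cut-points are from SAP 5.3. A row is reachable when the eligibility limit exceeds its cut-point.

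| Parameter (x ULN) | Eligible up to | Rows reachable | First row not reachable |
|---|---|---|---|
| ALT/AST, no liver metastases | <2.5 | none | >3 |
| ALT/AST, liver metastases | 5 | >3 | >5 |
| ALP | 2.5 | >1.5, >2 | >3 |
| Total bilirubin | 1 | none | >1 |
| Total bilirubin, Gilbert's syndrome | 3 | >1, >2 | no higher row listed |

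On Day 1 values alone, a combined transaminase-plus-bilirubin row needs liver metastases and Gilbert's syndrome in the same patient.

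**Step 3. Illustration with assumed values.** A patient with liver metastases has ALT 4.2 x ULN pre-dose on Day 1, 1.8 on Day 15 and 1.5 on Day 29.

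- Off drug at cut-off: max(4.2, 1.8, 1.5) = 4.2, counted as ALT >3 x ULN.
- Still on drug, by 2.5.6: max(1.8, 1.5) = 1.8, not counted.
- Still on drug, by Section 5: 4.2, counted.
- With one after-first-dose rule: 1.8 in every case, not counted.

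**Step 4. Which outputs are open to this.** The hepatic table and the shift tables without CTCAE grades depend on the on-treatment window and carry no separate after-baseline condition. The other safety outputs carry some wording of their own:

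- The first shift-table sentence in 5.3 refers to abnormal values after baseline.
- The listing of grade 3 or 4 values is limited to those after the start of treatment.
- The vital-sign criteria (5.4) all require a change from baseline, which the baseline record cannot show.
- The ECG categories (5.5) are new values or changes from baseline, and the ECG shift goes to the worst post-baseline value.
- The ECOG worst-score shift (5.6) is also to a post-baseline score.

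**The case against.** The best defence is that the problem is confined to a few descriptive tables. The trial has a single arm, SAP 2.2 plans no hypothesis test outside the primary endpoint, and every laboratory value is listed in chronological order, so a careful reader can find the pre-dose value. The Safety Set (SAP 3.1) already excludes anyone with no post-treatment safety data at all. The higher hepatic cut-points, which matter most clinically, are out of reach. All of this stands, and it limits the weight of the point. It does not remove it: a patient with other safety data but no later laboratory sample still enters the hepatic table on a pre-dose value alone, and a listing does not correct a summary count.

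A reader might infer that all laboratory counts by CTCAE grade are inflated, for instance by a patient who enters with hemoglobin of 9 g/dL. The documents do not establish that. The after-baseline wording in SAP 5.3 can be read as keeping the Day 1 baseline record out of the graded shift tables, and the grade 3 or 4 listing has its own limit. The reading is not secure, because protocol 10.5.3.1.2 describes the same shift tables by worst on-treatment value and the sentence on counts by grade has no qualifier of its own. That is an ambiguity, not a demonstrated double count.

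**Conclusion.** The point holds, for a limited set of outputs. The SAP places the first-dose date in both windows, never removes the baseline record from on-treatment, and contradicts itself on patients still on drug at cut-off. The consequence is clear for the hepatic threshold table, in the rows identified in Step 2, and for the shift tables of parameters without CTCAE grades.

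A count changes only if the patient had a Day 1 draw beyond the cut-point (or reference limit) and no later value beyond it. The documents do not give the baseline distribution, so the direction is known but the size is not.

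A reader might also infer that discontinued patients have Day 1 counted and ongoing patients do not. That follows from 2.5.6 alone. If Section 5 governs the tables, both groups are treated alike. What can be said is that the two sections conflict.

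The conclusion assumes that the Day 1 draw is taken before dosing, as the eligibility re-check and the glossary imply, and that patients meet the eligibility limits on that day. The clinical benefit analysis is not touched.

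**What to change.** In SAP 2.5.6 and Section 5, state one rule for all patients, ongoing or not:

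- On-treatment means after the first dose, judged by time where a time is recorded. For laboratory values without a time, it means Day 2 onward.
- The record selected as baseline is never also an on-treatment record.
- The hepatic threshold table and the shift tables for parameters without CTCAE grades use post-baseline values only.
- Adverse events keep their Day 1 start (SAP 5.1.3), and post-dose Day 1 ECGs stay on-treatment for everyone.

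The cost is a short definition and one programming condition. No post-dose laboratory sample is scheduled on Day 1, so no scheduled post-dose laboratory value is lost. Unscheduled tests are possible: protocol 7.2.2.5 allows extra laboratory examinations, and Table 6-5 calls for electrolytes when QT prolongation is found, which a Day 1 ECG could prompt. Such a value without a recorded time would be left out of the summaries but would still be listed. That is a small loss.

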2.5.7 Last contact date

The last contact date will be derived for patients not known to be dead at the analysis cut-off using the last complete date among the following:

- All assessment dates (e.g. vital signs assessment, performance status assessment). Note, only a true on study assessment date or patient contact date will be used. If there is a visit date without evidence of any actual assessment performed that date will not be used. No dates post cut-off will be used.
- Medication dates including study medications, and concomitant medications administered.
- Adverse event dates
- Last contact date collected on the 'Survival information' eCRF (only if the patient status is not unknown).
- The cut-off date will not be used for last contact date, unless an actual assessment or patient contact was performed.

Important note: imputed dates (e.g. the analysis cut-off date programmatically imputed to replace the missing end date of a dose administration record) will not be used to derive the last contact date, except for the following: partial date's imputation is allowed to be used for

event (death) and for censoring date only if coming from Survival Information page.

The last contact date will be used for censoring of patients in the analysis of overall survival.

2.5.8 Year, month and week

For reporting purpose below mentioned rule will be followed to convert a year, month and week in days.

1 year = 365.25 days

1 month = 30.3475 days

1 week = 7 days

3 Patients and treatments

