3.3 Patient disposition

The FAS analysis set will be used for patient disposition summaries. Following categories will be summarized:

1. Number (%) of patients who are treated
2. Number (%) of patients who are still on treatment
3. Number (%) of patients who discontinued study drug
4. Reasons for discontinuation of study drug
5. Number (%) of patients who consent to be followed for survival follow-up

6. Number (%) of patients who lost to follow-up during survival follow-up period (Note: it is defined as the patients whose last known survival status based on the survival follow-up contact occurred more than 6 months before the cut-off date)

For patients who were screened but did not take the study treatment, a listing with reasons for screen failure will be provided.

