3.4 Patient background, demographics and baseline characteristics

Demographic and baseline characteristics data, disease characteristics, medical history, and prior anti-neoplastic therapies are collected at the screening visit. Descriptive summaries and/or listings will be provided. The FAS analysis set will be used for the presentation.

Demographic and baseline characteristics

Demographic characteristic variables include:

- Age (years), age group (<65 and \geq 65; <75 and \geq 75 years)
- Sex (Male, Female)
- Race (White, Black or African American, Asian, Other [including American Indian or Other Alaska Native, Native Hawaiian or Other Pacific Islander, and Other])

Baseline characteristic variables include:

- Height and weight
- ECOG performance status
- Cardiac imaging (Left Ventricular Ejection Fraction [LVEF])

Disease characteristics

Disease characteristic variables include:

- Primary tumor type (**Sponsor adjudicated**)
Note: The tumor type adjudication is made based on the combination of the primary site of tumor with the tumor histology/cytology as collected in the CRFs.
- Time (in months) from initial diagnosis to the first dose of ribociclib
- Time (in months) from date of most recent recurrence/relapse to the first dose of ribociclib
- Presence of B symptoms (for lymphoma patients only)
- Stage at initial diagnosis
- Prior lines of antineoplastic medication therapy
- Prior lines of chemotherapy
- Prior antineoplastic radiotherapy (yes/no)
- Prior antineoplastic surgery (yes/no)

Other patient characteristics

- Gene mutations as detected by local and central labs in pre-defined per-protocol mutation categories

- Age of biopsy samples (in months) calculated from date of biopsy sample date to the first dose of ribociclib

Medical history

Medical history and ongoing conditions, including cancer-related conditions and symptoms will be summarized and listed. The summaries will be presented by primary system organ class and preferred term. Medical history/current medical conditions are coded using the Medical dictionary for regulatory activities (MedDRA) terminology (v18.0). A separate summary will be presented for ongoing medical conditions by severity of the condition (i.e., grade 1 to grade 4).

Prior anti-neoplastic therapies

Prior anti-neoplastic therapies will be listed in three separate listings:

- Medications
- Radiotherapy
- Surgery

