3.5.1.1 Duration of exposure

Duration of exposure (days) for study drug is defined as the days between the last ribociclib dose and first ribociclib dose, that is to say, duration of exposure (D1) = (date of last administration of ribociclib) – (date of first administration of ribociclib) + 1. Summary statistics will be displayed for the duration of exposure.

Duration of exposure to study drug will also be categorized into time intervals (< 3 months, 3 – < 6 months, 6 – < 9 months,..., etc.). The number and percentage of patients in each category will be presented.

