4.4 Progression Free Survival (PFS)

PFS is defined as the time from the date of first dose of ribociclib to the date of the first documented disease progression/relapse or death due to any cause within 30 days of the last study drug dose date, and is calculated as $PFS = (\text{date of progression/relapse or death} - \text{date of first study treatment} + 1)$. Disease progression noted as the reason for discontinuation of treatment will also be considered as a progression event for PFS analyses.

Patients who discontinue or complete study treatment without disease progression will be censored at last adequate tumor assessment on or before the discontinuation/completion of the study. For patients who are still on study treatment at the time of data cut-off date for the primary analyses, PFS will be censored at the last adequate tumor assessment before the data cut-off date for the analysis of PFS for the primary CSR. Patients who do not have any post baseline tumor assessment will be considered as censored at Day 1.

PFS will be summarized and graphed using the Kaplan-Meier product-limit method². The estimated median survival time, the corresponding 95% CIs³, and 25th and 75th percentiles will be provided. In addition, survival-rate estimates with 95% CIs will also be provided at time points, such as 1, 2, 3, 4, 5, 6, 9 and 12 months. Analyses will be based on all tumor types combined. For tumor types that have ten (10) or more patients, separate summaries will be performed by the tumor type.

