4.5 Overall Survival (OS)

Overall survival, defined as the time from the date of the first dose of ribociclib to the date of death due to any cause will be analyzed using methods similar to those stated above for PFS. That is, the 25th percentile, median, and 75th percentile of survival time with corresponding 95% CIs will be provided; survival curve and survival rates at time points, such as 3, 6, 9, 12, 18, and 24 months will also be presented. Patients who are alive at the time of discontinuation/completion of the study will be censored at the last contact date (as defined in Section 2.5.7). Analyses will be based on all tumor types combined. For tumor types that have ten (10) or more patients, separate summaries will be performed by the tumor type.

Handling missing month/day in date of death

For rare cases when either day is missing or both month and day are missing for the date of death, the follow imputation rules will be implemented:

- If only day is missing, then impute maximum of [(1 mmm-yyyy), minimum of (any valid date from data base used for deriving last contact date + 1, cut-off date)].
- If both day and month are missing, then impute maximum of [(1 Jan-yyyy, minimum of (any valid date from data base used for deriving last contact date + 1, cut-off date)].

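### SAP 2.5.8 sets a month at 30.3475 days, which contradicts its own 365.25-day year (365.25/12 = 30.4375); if programmed as written, values in months come out 0.3% too long

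*SAP*

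**What the plan says.** SAP 2.5.8 introduces its constants as a rule to be applied: "For reporting purpose below mentioned rule will be followed to convert a year, month and week in days". It then gives "1 year = 365.25 days", "1 month = 30.3475 days" and a week of 7 days. Neither the SAP nor the protocol gives any other month length.

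Months appear explicitly in these SAP outputs:

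- **3.3, disposition:** loss to survival follow-up means a last known status that "occurred more than 6 months before the cut-off date".
- **3.4, baseline:** "Time (in months) from initial diagnosis to the first dose of ribociclib". Time from most recent relapse and age of the biopsy sample are also in months.
- **3.5.1.1, exposure:** the duration itself is defined in days, but "Duration of exposure to study drug will also be categorized into time intervals (< 3 months, 3 – < 6 months, 6 – < 9 months,..., etc".
- **4.4, PFS:** the time is a difference of dates plus one day, with rates "at time points, such as 1, 2, 3, 4, 5, 6, 9 and 12 months".
- **4.5, OS:** "survival curve and survival rates at time points, such as 3, 6, 9, 12, 18, and 24 months will also be presented".

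No unit is stated for median PFS, median OS or duration of response.

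**The concern.** Two constants in the same short list disagree. A conversion constant in an analysis plan is there to be copied into code, so the slip would carry into each output that uses it. A programmer who follows the SAP obtains months that do not add up to the SAP's own year. A programmer who uses 365.25/12 departs from the written plan, and two people working independently could produce outputs that do not match. At stake are the accuracy of month-valued summaries and the day at which each month landmark or category boundary falls.

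**Working it through.** **Inputs (SAP 2.5.8):** year Y = 365.25 days; stated month m = 30.3475 days. Landmarks are from SAP 4.4 and 4.5, and boundaries from SAP 3.3 and 3.5.1.1.

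**1. Can the stated month be reproduced?**

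- From the SAP's year: 365.25/12 = 30.4375.
- From a 365-day year: 365/12 = 30.4167.
- From thirteen 28-day cycles: 13 × 28/12 = 30.3333.

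None gives 30.3475. Swapping the first two digits after the decimal point turns 30.3475 into 30.4375, the first result exactly.

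**2. Size of the contradiction.** 12 × 30.3475 = 364.17 days, and 365.25 − 364.17 = 1.08 days short of the stated year. One stated year converts to 365.25/30.3475 = 12.036 months.

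**3. Effect on values in months.** The ratio is 30.4375/30.3475 = 1.00297, an overstatement of 0.3%. Examples:

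- 730.5 days: 24.07 months instead of 24.00.
- 1826.25 days (5 years): 60.18 instead of 60.00.
- 3652.5 days (10 years): 120.36 instead of 120.00.

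**4. Effect on landmarks and boundaries.** At k months the shift is k × (30.4375 − 30.3475) = 0.09k days. The last two columns give the last whole day inside the limit.

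| Months | k × 30.3475 | k × 30.4375 | Early by (days) | Last day, stated | Last day, consistent |
|---|---|---|---|---|---|
| 1 | 30.3475 | 30.4375 | 0.09 | 30 | 30 |
| 2 | 60.695 | 60.875 | 0.18 | 60 | 60 |
| 3 | 91.0425 | 91.3125 | 0.27 | 91 | 91 |
| 4 | 121.39 | 121.75 | 0.36 | 121 | 121 |
| 5 | 151.7375 | 152.1875 | 0.45 | 151 | 152 |
| 6 | 182.085 | 182.625 | 0.54 | 182 | 182 |
| 9 | 273.1275 | 273.9375 | 0.81 | 273 | 273 |
| 12 | 364.17 | 365.25 | 1.08 | 364 | 365 |
| 18 | 546.255 | 547.875 | 1.62 | 546 | 547 |
| 24 | 728.34 | 730.50 | 2.16 | 728 | 730 |

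The three exposure limits that the SAP names (3, 6 and 9 months) therefore classify the same patients under either constant, and so does the 6-month loss-to-follow-up rule. If the three-month bands continue to 12 months, which the SAP implies but does not list, a patient exposed for 365 days is at 365/30.3475 = 12.03 months instead of 365/30.4375 = 11.99, and moves up one band.

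**5. Which landmarks can be reached at the primary cut-off?** Protocol Amendment 3 says that the study began in August 2014 and closed to enrolment on 8 May 2015. SAP 2.2 places the cut-off where the last patient on treatment completes four cycles, which is 4 × 28 = 112 days after first dose. Assume that the last patient was first dosed between 8 May and 28 days later (the screening window). The cut-off is then between 28 August and 25 September 2015. Counted from 1 August 2014, the longest possible follow-up is 392 to 420 days, or 392/30.4375 = 12.9 to 420/30.4375 = 13.8 months. The 18- and 24-month OS landmarks lie beyond that.

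**The case against.** The strongest reply is that this is a typing slip with no bearing on any conclusion. Much of that stands. The primary endpoint is defined at 16 weeks (SAP 4.1), and the 7-day week is right. All other analyses are descriptive (SAP 2.2). Changing the unit leaves event times in days, their order and the curve shape as they were. Scans are due every 8 weeks and then every 16, within 4 days either way (Protocol 4.1.1), so a one-day shift in a PFS landmark is smaller than the visit window.

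Two stronger readings are tempting, and the documents support neither.

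- A reader might infer that every reported duration is wrong. The documents show the plan's text, not the constant that was programmed, so the effect is conditional. Duration of exposure and the PFS formula are worked in days. Duration of response has no stated unit and is only listed if there are too few events (SAP 2.3 and 4.3).
- A reader might infer that month cut-offs in general fall two days early. Two days arises only at the 24-month OS landmark, which the primary report cannot reach. It could matter only in later OS reporting, and the sponsor may stop survival follow-up if the primary endpoint is not met (Protocol 7.1.4.3).

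The reply does not remove the contradiction. Both figures stand in one list, the list is a rule to be followed, and nothing elsewhere repairs it.

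**Conclusion.** The point holds as a minor internal error. That the two constants contradict each other is certain from SAP 2.5.8 alone. That digits were transposed is an inference, but a strong one, because the swap recovers 365.25/12 exactly.

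The size depends on the SAP value being programmed as written. Under that assumption, month-valued results are 0.3% too long. At the primary report, the only listed landmarks that move in whole days are 5 months (PFS) and 12 months (PFS and OS), by one day each. The 18-month OS point would move by one day and the 24-month point by two, in later reporting only. The claim that these two lie out of reach at the primary cut-off rests on the enrolment dates in Amendment 3 and the assumed first-dose window above. No success decision is affected.

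**What to change.** In SAP 2.5.8, replace 30.3475 with 30.4375, so that twelve months equal the stated 365.25-day year. Then check that the conversion constant in the analysis programs is 30.4375. If outputs were already produced with 30.3475, rerun those that convert to or from months. The cost is one number in the SAP and one constant in the code; no design element or decision rule changes.
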